1.2.1. Rationale for Study Design

This prospective study will use a head to head design for 30 participants, 60 eyes. All eyes will receive bilateral Restasis. The study group will consist of 20 eyes receiving DEXTENZA® insertion. The control groups will consist of 20 eyes receiving Lotemax and 20 eyes will have Restasis monotherapy.

2. STUDY OBJECTIVES

2.1. Primary Objective

- Mean change in ocular surface staining (sodium fluorescein and lissamine green) from baseline at week 1, week 2, week 4, week 8 and week 12 as measured by the NEI grading scale

2.2. Secondary Objectives

- Mean change in MMP-9 from baseline at week 1, week 2, week 4, week 8 and week 12 as measured by InflammaDry
- Mean change in tear break-up time (TBUT) from baseline at week 1, week 2, week 4, week 8 and week 12
- Mean change in conjunctival injection from baseline at week 1, week 2, week 4, week 8 and week 12 as measured on a scale of 0-4 and graded by the physician
- Change from baseline in meibomian gland scores (expressibility and quality) at week 1, week 2, week 4, week 8 and week 12.
- Mean change in tear osmolarity from baseline at week 1, week 2, week 4, week 8 and week 12 as measured by Tear Lab
- Mean change in DEQ-5 from baseline at week 1, week 2, week 4, week 8 and week 12
- Mean change in Best-corrected Visual Acuity (BCVA) from baseline at week 1, week 2, week 4, week 8 and week 12 as measured by ETDRS chart
- Mean change in Schirmer's score from baseline at week 1, week 2, week 4, week 8 and week 12 as measured by Schirmer's test strip

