1. INTRODUCTION AND RATIONALE

1.1. Introduction

Dry eye disease (DED) is a multifactorial disorder of the ocular surface that severely impacts vision and quality of life. Risk factors that contribute to DED include age, gender, hormones, autoimmune disorders, local environment, use of video displays, contact lens wear and exposure to medications/preservatives, all potentially leading to secretory or evaporative DED, or both.¹ The Tear Film and Ocular Surface Society's Dry Eye Workshop II definition recognizes the impact of inflammation, saying, "Dry eye is a multifactorial disease of the ocular surface characterized by a loss of homeostasis of the tear film, and accompanied by ocular symptoms, in which tear film instability and hyperosmolarity, ocular surface inflammation and damage, and neurosensory abnormalities play etiological roles."²

Topical cyclosporine A (Restasis) is indicated to increase tear production in patients whose tear production is presumed to be suppressed because of ocular inflammation associated with DES. A significant number of studies are available concerning the use of cyclosporine as a way to modulate inflammation. Positive effects are consistently seen with the use of this drug for treatment of DES.³ Topical application exerts a therapeutic effect without causing systemic side effects, because only small amounts can penetrate into the bloodstream after topical application.⁴

After determining the severity of the inflammation in a DED patient, the doctor can then decide if a topical steroid is needed to quickly decrease the overall inflammation along with Restasis.

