3. STUDY DESIGN

3.1. Study Description and Duration

This prospective, open-label, single-center, non-randomized, investigator-sponsored clinical study seeks to investigate the benefit of managing patients with DED with a sustained release intracanalicular dexamethasone (0.4 mg) insert in addition to Restasis compared to Restasis in conjunction with Lotemax and Restasis alone. In addition, this study will evaluate the ease of DEXTENZA® insertion.

After screening a given patient for inclusion and exclusion criteria, and gaining informed consent, both eyes will be prescribed Restasis. Both eyes of 10 patients will be selected to receive DEXTENZA® insertion (study group), while 10 patients will be prescribed Lotemax and 10 patients will be on Restasis monotherapy (control groups). Per patient, the study period will last for approximately 12 weeks after the DEXTENZA® insertion, consisting of one screening/prescription visit and 5 post-procedure follow-up visits (week 1, week 2, week 4, week 8 and week 12). At week 1, week 2, week 4, week 8 and week 12, primary and secondary endpoints will be assessed alongside standard-of-care procedures. Adjusting for enrollment period, the study will last a total of approximately 9 months.

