### **Main Outcome Measures**

The primary outcome measure was the mean change in corneal surface staining (guided by use of fluorescein and lissamine green) at weeks 1, 2, 4, 8 and 12 based on the NEI grading scale. Corneal fluorescein staining was graded from 0 to 3 (none to heavy) in five regions of the cornea and summed for a total score.

All secondary outcome measures followed the same timeline with comparison at weeks 1, 2, 4, 8 and 12 in comparison to baseline. Secondary outcome measures included the mean change in tear break-up time (TBUT), the mean change in conjunctival staining (graded 0-3 in 6 regions), the mean change in tear osmolarity as measured by TearLab, the mean change in DEQ-5, the mean change in meibomian gland scores as measured by quality of meibum expression, the mean change in best-corrected distance visual acuity (BCDVA) as measured by ETDRS chart and the mean change in Schirmer's score as measured by a Schirmer's test strip.

Meibomian gland scoring involved grading the quality of expression (0-3) from 15 glands along the lower eyelid including temporal, central and nasal. For scoring, 3 was representative of clear, liquid secretions and 0 was no secretions. The DEQ-5 Dry Eye Questionnaire was used to evaluate symptoms and characterize severity of discomfort, dryness and tearing. Possible scores ranged from 0 to 22 with higher scores representing worse symptoms.

On the screening visit and the initiation of therapy including implantation of the dexamethasone insert in the study group, a physician ease of insertion questionnaire was also completed by the physician implanting the device. All device-related complications were recorded. All subject-reported adverse events were recorded at each study visit.

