## **RESULTS**

### **Patient Demographics**

Sixty eyes of 30 subjects were successfully enrolled into the study including 20 eyes of 10 subjects in the dexamethasone/cyclosporine group, 22 eyes of 11 subjects in the loteprednol/cyclosporine group and 18 eyes of 9 subjects in the cyclosporine monotherapy group. All 3 groups were summarized by baseline characteristics, which are shown in Table 2.

None of the three groups, including the study and two control groups met the primary endpoint. In the dextenza group, the mean baseline corneal staining score was  $0.5 \pm 1.0$  with 70% ( $n=14$ ) without evidence of corneal staining at baseline. The mean score at weeks 4, 8 and 12 was  $0.6 \pm 1.0$  ( $P = 0.99$ ),  $0.5 \pm 1.1$  ( $P = 0.99$ ) and  $0.7 \pm 1.4$  ( $P = 0.97$ ), respectively. In the loteprednol group, the mean baseline corneal staining score was  $0.8 \pm 1.5$  with 64% ( $n=14$ ) without corneal staining at baseline. At weeks 4, 8 and 12, the mean score was  $0.9 \pm 0.9$  ( $P = 0.99$ ),  $0.0 \pm 0.0$  ( $P = 0.06$ ) and  $0.6 \pm 1.0$  ( $P = 0.78$ ), respectively. In the cyclosporine monotherapy group, the mean baseline corneal staining score was  $0.5 \pm 0.5$  with 50% ( $n=9$ ) of eyes absent of any corneal staining at baseline. There was no significant change in corneal staining at any time point with a mean score of  $1.1 \pm 1.4$  ( $P = 0.26$ ),  $0.3 \pm 0.6$  ( $P = 0.63$ ) and  $0.5 \pm 0.7$  ( $P = 0.99$ ) at weeks 4, 8 and 12, respectively. These results, in addition to comparisons of other outcome measures, are summarized in Table 3.

There was no significant change in conjunctival staining, Schirmer scores, TBUT, tear osmolarity or meibomian gland scores at any of the follow-up time points in comparison to baseline in all three groups. These results are summarized and also demonstrated in Table 3.

Across all visits, the mean IOP remained stable in all three groups. In the cyclosporine monotherapy group, there were no instances of IOP elevation  $>10$  mmHg above baseline. Similarly, in the dextenza and loteprednol groups, there were no instances of IOP elevation  $>10$

mmHg above baseline at any time point. There were no canalicular-related complications or adverse events related to implantation of the dexamethasone insert. No patients required removal of the insert.

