## CONCLUSION

The challenges of topical medication use are widespread and well recognized across ophthalmology. The safety profile reported in this study, albeit a small sample size, indicates the dexamethasone intracanalicular insert is a safe alternative option to topical steroids to augment the anti-inflammatory properties of topical cyclosporine 0.05%. Further study is necessary but use of the dexamethasone insert may provide a means to optimize medication delivery without compromising safety or efficacy in the treatment of dry eye disease.

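### MMP-9 and conjunctival injection, two protocol secondary endpoints, are absent from the SAP without explanation, and visual acuity and ease of insertion have no reported result

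*Protocol*

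**What the plan says.** Protocol section 2.2 lists eight secondary endpoints. They include "Mean change in MMP-9 from baseline at week 1, week 2, week 4, week 8 and week 12 as measured by InflammaDry" and "Mean change in conjunctival injection from baseline at week 1" and at each later visit, the latter on a physician-graded 0-4 scale. Best-corrected acuity on the ETDRS chart is also on the list. The synopsis names the same three. The Schedule of Events (Table 1), section 5.1.1 and the appendices place MMP-9 and injection at all six visits, and the appendices anchor every injection grade in words.

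Ease of insertion is a further aim in section 3.1: "In addition, this study will evaluate the ease of DEXTENZA® insertion". The appendices give its form, a 0 to 10 scale completed on the day of insertion.

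The SAP, under Main Outcome Measures, gives a different list: "Secondary outcome measures included the mean change in tear break-up time (TBUT), the mean change in conjunctival staining (graded 0-3 in 6 regions"), then tear osmolarity, DEQ-5, meibomian gland score, "the mean change in best-corrected distance visual acuity (BCDVA) as measured by ETDRS chart", and Schirmer's score. The same section says that the insertion questionnaire was filled in by the implanting physician. The results text says: "There was no significant change in conjunctival staining, Schirmer scores, TBUT, tear osmolarity or meibomian gland scores" at follow-up in any group. It also covers corneal staining, IOP, device complications and DEQ-5. The Conclusion, reasoning from the safety profile, describes the insert as a safe alternative to topical steroids "to augment the anti-inflammatory properties of topical cyclosporine 0.05"%.

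**The concern.** When a protocol fixes a list of secondary endpoints and the analysis document covers only part of it without comment, the reader cannot separate four situations: the missing outcome showed nothing, went the wrong way, went the right way, or was never measured. That ambiguity is the usual route by which outcome-reporting bias enters a record, whatever the reason for the gap.

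Two of the missing measures matter more than the others. The SAP's Introduction treats inflammation as central to dry eye and presents the study as the first to use the insert against it. MMP-9 and injection are the endpoints that come closest to observing inflammation. Without them, a sentence about augmenting an anti-inflammatory effect has no direct inflammation finding from this trial beside it.

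**Working it through.** No sample-size, power or error-rate figure is involved. The check sets the protocol's list beside the SAP's list and the SAP's results.

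| Protocol 2.2 secondary endpoint | In SAP outcome list? | Result in SAP text or tables? |
|---|---|---|
| MMP-9 (InflammaDry) | No | No |
| TBUT | Yes | Yes |
| Conjunctival injection (0-4) | No | No |
| Meibomian gland score | Yes (quality only) | Yes |
| Tear osmolarity | Yes | Yes |
| DEQ-5 | Yes | Yes (text) |
| Best-corrected acuity | Yes | No |
| Schirmer's score | Yes | Yes |

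1. Kept in the SAP list: 8 − 2 = 6. The SAP names seven secondary measures because it adds conjunctival staining: 6 + 1 = 7.
2. With a result: 6 − 1 (acuity) = 5. Without a result: 8 − 5 = 3.
3. Ease of insertion is outside the eight. It is an aim in section 3.1, the SAP says the form was completed, and no score is given. It adds one unreported item.
4. Conjunctival staining does not stand in for injection. Under protocol section 2.1 and Appendix I, lissamine green staining of the conjunctiva belongs to the primary endpoint. Injection is a separate grading of vessel dilation and redness in Appendix II.
5. Elsewhere in the available SAP text, MMP-9 occurs only in the title of a cited paper, and conjunctival redness only as a side effect of cyclosporine.
6. Planned volume: 30 patients × 6 visits = 180 patient-visits for each of MMP-9 and injection. This is what was scheduled. The documents do not show how much was collected.
7. Table numbering: the results text cites Table 2 for baseline data and Table 3 for outcomes, while the tables shown are labelled 1 and 2. Both references are off by one, which points to a numbering shift and not to a further table holding the missing outcomes.

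The count depends slightly on which protocol list is used. The synopsis names SPEED where section 2.2 names DEQ-5. SPEED has no SAP result either, so the synopsis would give 4 of 8. SPEED is not in the Schedule of Events, so I count from section 2.2.

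**The case against.** The strongest reply concerns the Conclusion. It is a safety statement, and the phrase about augmenting cyclosporine can be read as describing what steroids are used for, a use the Discussion attributes to prior studies. The Discussion concedes that efficacy remains unclear, and the Conclusion calls for further study. This stands. The Conclusion does not claim that the trial demonstrated an anti-inflammatory effect. What remains is narrower: the phrase has no direct inflammation result from this trial behind it, and the efficacy caveat does not tell the reader that planned endpoints are missing.

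A second reply is that inflammation was not what the trial set out to test. The synopsis objective concerns signs and symptoms, the hypotheses in section 1.2 concern symptoms and non-inferiority, and the primary endpoint is staining. Section 1.1 only leaves it to the doctor to judge whether "a topical steroid is needed to quickly decrease the overall inflammation along with Restasis", a remark about practice in general. This also stands. It lowers the weight of the point but does not explain why listed endpoints are absent.

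Third, no document labels MMP-9 and injection as the direct inflammation measures. That is my inference from what the other endpoints record: staining, tear film, glands, symptoms and acuity.

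Fourth, the part of the SAP before its Introduction was not available. An explanation could lie there, although the methods, results and tables, where these outcomes would be expected, were all available.

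Fifth, the list is not perfectly clean. The appendix gives DEQ-5 a visit numbering that differs from Table 1, and the SAP scores meibomian quality but not expressibility. Neither affects the three endpoints without a result. The reported absence of canalicular complications, insertion-related events and removals is informative, but it is not the ease-of-insertion score.

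**Conclusion.** The omission is established for the available SAP text: 3 of the 8 secondary endpoints in section 2.2 (MMP-9, conjunctival injection, best-corrected acuity), plus the ease-of-insertion aim, have no result. MMP-9 and injection are also missing from the outcome list itself, without explanation.

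A reader might infer that unfavourable inflammation data were withheld, or that the trial draws an anti-inflammatory conclusion against its own evidence. The documents support neither. They show that the measures were scheduled, not that they were collected. They give no reason for the gap, and the Conclusion argues from safety.

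The finding rests on two assumptions: that the unavailable opening part of the SAP does not account for these outcomes, and that MMP-9 and injection are the endpoints nearest to inflammation. The count needs only the first. The comment on the Conclusion's wording needs both. The endpoints are secondary, so this should be corrected but does not change the primary result.

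**What to change.** - Report MMP-9, conjunctival injection and best-corrected acuity by group at baseline and at weeks 1, 2, 4, 8 and 12. The present results table shows only baseline and weeks 4, 8 and 12.
- Report the 0-10 ease-of-insertion score for the insert group.
- For any measure not collected or not analysed, say so, give the reason, and label it a departure from protocol section 2.2, or from section 3.1 for ease of insertion.
- Identify MMP-9 and injection as secondary endpoints on the authority of the protocol. The SAP is written in the past tense with results in hand, so adding them to its list now would not by itself make them prespecified.
- In the Conclusion, mark the anti-inflammatory phrase as a hypothesis or as resting on prior studies.

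No new patients or visits are needed. Where the data exist, the cost is a little more analysis and a few table rows; where they do not, it is a sentence or two. The results may turn out to be unfavourable.

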1.2. Rationale

Although Restasis works as an anti-inflammatory, by preventing T-cells from releasing cytokines and increases tear production in patients whose tear production is presumed to be suppressed due to ocular inflammation associated with keratoconjunctivitis sicca, we hypothesize that the addition of DEXTENZA® will provide greater symptomatic improvement than pharmacotherapy alone. Additionally, we hypothesize that the addition of DEXTENZA® will show non inferiority in comparison to Restasis in combination with Lotemax.

This study will compare and evaluate the benefit of treatment with a physician administered intracanalicular dexamethasone insert (0.4 mg) bilaterally, compared to Lotemax prescribed ~~BID~~, in patients that are prescribed Restasis bilaterally to increase tear production in patients with aqueous deficient DED. In addition, the study will evaluate physician assessment of ease of DEXTENZA® insertion.

Drug delivery platforms are an innovative exciting advancement in ophthalmology. They allow patients to eliminate topical medications which are generally associated with lack of compliance, difficulty of use and requiring help from family members. At times, patients may have to take several drops, increasing the likelihood of non-compliance and adding a level of complexity to their drop regimen.

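### The planned head-to-head has no between-arm model with a baseline covariate, and against loteprednol several signs change direction between mean change and final value

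*Protocol*

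**What the plan says.** Protocol 1.2.1 sets out the comparative aim: "This prospective study will use a head to head design for 30 participants, 60 eyes". Protocol 1.2 hypothesises greater symptomatic improvement than with pharmacotherapy alone and, for the loteprednol arm, that "the addition of DEXTENZA® will show non inferiority in comparison to Restasis in combination with Lotemax". No margin is given.

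The endpoints are raw changes. Protocol 2.1 has "Mean change in ocular surface staining (sodium fluorescein and lissamine green) from baseline", and 2.2 uses the same form throughout, as in "Mean change in tear osmolarity from baseline at week 1, week 2, week 4, week 8 and week 12 as measured by Tear Lab". SAP Main Outcome Measures keeps that form.

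SAP Statistical Analysis specifies repeated-measures ANOVA within each group, then Bonferroni-corrected tests of each visit against that group's own baseline. It has no arm term and no covariate. Even so, the SAP Discussion describes the two steroid groups as giving similar results, and the Conclusion suggests that the insert may improve delivery at no cost in efficacy.

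On allocation, Protocol 3.1 describes "This prospective, open-label, single-center, non-randomized, investigator-sponsored clinical study" and has patients selected for the insert. SAP Patients and SAP Discussion call the study randomized.

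On baseline data, the SAP Results text says "All 3 groups were summarized by baseline characteristics, which are shown in Table 2". The demographics table is in fact labelled Table 1 and holds age, race, gender and IOP. Baselines for six efficacy measures are in the results table (Table 2), and the DEQ-5 baseline is in the Results text.

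**The concern.** A difference in mean change equals the difference in final values minus the baseline gap. If two arms start apart, a comparison of raw changes subtracts the whole gap, and a comparison of final values subtracts none of it. A baseline-adjusted estimate subtracts the part that the data support. The plan commits to none of the three for comparing arms.

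At stake is the comparison that the protocol says it is for. With 9 to 11 patients per arm, sizeable baseline gaps are likely under any allocation method. A reader who compares the printed mean changes by eye, as the Discussion and Conclusion invite, can reach the opposite conclusion from one who compares the printed final values.

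**Working it through.** The documents state no between-arm figure, so there is none to reproduce. All inputs are means ± SD from SAP Table 2, with DEQ-5 from the SAP Results text. Weeks 1 and 2 are not tabulated. Gaps are insert minus loteprednol.

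**Step 1: baseline gaps.** Standardised gap = mean difference / sqrt((s1² + s2²)/2). For osmolarity: -15.8 / sqrt((17.4² + 19.8²)/2) = -15.8 / 18.64 = -0.85.

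| Measure | Insert | Loteprednol | Gap | Standardised |
|---|---|---|---|---|
| Osmolarity | 295.5 ± 17.4 | 311.3 ± 19.8 | -15.8 | -0.85 |
| Meibomian score (higher is better) | 8.7 ± 2.4 | 7.1 ± 2.1 | +1.6 | +0.71 |
| TBUT | 6.6 ± 2.2 | 5.4 ± 1.5 | +1.2 | +0.64 |
| Conjunctival staining | 0.5 ± 1.8 | 1.5 ± 1.8 | -1.0 | -0.56 |
| Schirmer | 14.9 ± 10.3 | 10.3 ± 7.2 | +4.6 | +0.52 |
| Corneal staining | 0.6 ± 1.0 | 0.8 ± 1.5 | -0.2 | -0.16 |
| DEQ-5 | 14.1 ± 4.0 | 14.4 ± 2.4 | -0.3 | -0.09 |

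Two inputs need care. The TBUT baseline row is identical in all three arms to the IOP row of SAP Table 1, so one of them is probably miscopied. The Results text gives the insert arm's corneal baseline as 0.5, which makes that gap -0.3 (standardised -0.24).

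**Step 2: change against final value.** Difference in change = difference in final value - baseline gap. For osmolarity at week 12: final 299.5 - 304.4 = -4.9; change -4.9 - (-15.8) = +10.9.

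| Measure | Difference in change, weeks 4 / 8 / 12 | Difference in final value, weeks 4 / 8 / 12 | Sign differs |
|---|---|---|---|
| Osmolarity | +12.5 / +19.6 / +10.9 | -3.3 / +3.8 / -4.9 | weeks 4, 12 |
| Schirmer | -2.1 / -1.2 / -2.4 | +2.5 / +3.4 / +2.2 | all three |
| Conjunctival staining | +0.4 / +0.6 / +0.8 | -0.6 / -0.4 / -0.2 | all three |
| Meibomian score | -0.7 / +0.4 / +1.1 | +0.9 / +2.0 / +2.7 | week 4 |
| TBUT | +0.7 / +0.3 / +0.4 | +1.9 / +1.5 / +1.6 | none |
| Corneal staining | -0.1 / +0.7 / +0.3 | -0.3 / +0.5 / +0.1 | none |
| DEQ-5 | -0.1 / +2.5 / +0.4 | -0.4 / +2.2 / +0.1 | none |

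**Step 3: what adjustment would do.** Adjusted difference = difference in final value - b × baseline gap, where b is the within-arm slope of the visit value on baseline. The documents do not give b, so 0.3, 0.5 and 0.7 are assumed.

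- Osmolarity, week 12: -4.9 + 15.8b = -0.2, +3.0, +6.2.
- Osmolarity, week 8: 3.8 + 15.8b = +8.5, +11.7, +14.9.
- Schirmer, week 12: 2.2 - 4.6b = +0.8, -0.1, -1.0.
- Conjunctival staining, week 12: -0.2 + 1.0b = +0.1, +0.3, +0.5.

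The raw change exceeds the adjusted value by (1 - b) × gap: 4.7 to 11.1 of the 15.8 osmolarity units over this range of b.

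**Step 4: could the gaps be chance?** For baseline osmolarity, a Welch test gives p = 0.009 counting 20 and 22 eyes, and p = 0.067 counting 10 and 11 patients. Counting patients, 0.067 is the smallest p among these measures.

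**Step 5: precision.** The standard error of the week 12 osmolarity difference in final values, counting patients, is sqrt(16.2²/10 + 28.7²/11) = 10.1. The final-value difference of -4.9 is therefore under one standard error. The reversals are in point estimates.

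**The case against.** The strongest objection is that the SAP makes no between-arm test. A within-arm test against baseline carries no between-arm gap, so the printed P values are not biased in this way. That stands: the first defect is the missing between-arm model, and the covariate is part of repairing it. Nor is mean change wrong as an outcome. With baseline as covariate, modelling the change or the visit value gives the same arm effect.

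Four stronger readings might be inferred, and the documents do not support them.

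- **The insert arm is the mildest of the three.** Monotherapy is milder on conjunctival staining (0.4 against 0.5) and meibomian score (9.2 against 8.7).
- **All endpoints start far apart.** The SAP's primary corneal score and DEQ-5, which bears on the symptom hypothesis, start close. Conjunctival staining is secondary in the SAP, although Protocol 2.1 includes lissamine green staining in its primary objective.
- **Steroid went to the more inflamed patients.** Protocol 1.1 says "the doctor can then decide if a topical steroid is needed to quickly decrease the overall inflammation along with Restasis", but this is background on practice and not an allocation rule. On that account the insert arm should start worse than monotherapy. It starts better on osmolarity (295.5 against 306.9), Schirmer (14.9 against 11.6) and, as printed, TBUT (6.6 against 5.7).
- **The arms were certainly selected.** The SAP says randomized. If so, the gaps are chance, raw change is unbiased over repeated allocation, and adjustment mainly adds precision and deals with the imbalance that occurred.

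It is also fair that, if arms were selected, raw change and baseline adjustment rest on different untestable assumptions, and neither is known to be free of bias.

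**Conclusion.** The point holds for the comparison that the protocol intends and that the SAP draws informally. It does not touch the within-arm tests. Against loteprednol, the insert arm starts milder by about 0.5 to 0.85 standard deviations on four signs, and on TBUT (0.64) if that row is right. For osmolarity at two of three tabulated visits, and for Schirmer and conjunctival staining at all three, the choice between unadjusted change and final value decides which arm looks better. Corneal staining and DEQ-5 are little affected.

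The gaps and reversals follow directly from the printed means. The adjusted figures rest on the assumed slopes of 0.3 to 0.7, and adjustment does not always side with the final value: for week 12 conjunctival staining it stays on the side of the change. Neither direction is evidence that one arm is better.

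**What to change.** - In SAP Statistical Analysis, add a between-arm model for each endpoint and visit: the visit value on arm, with the baseline value of the same measure as the only covariate. Fit it on patient means of the two eyes, or with eyes nested within patients. Give each arm difference with a 95% CI and the unadjusted difference in change beside it. Because the SAP document already carries results, label the model as added after they were known.
- Reconcile Protocol 3.1 (non-randomized) with SAP Patients and Discussion (randomized). State that, if arms were selected, adjustment reduces bias but does not guarantee its removal.
- Treat the linear model with caution for corneal staining: 70%, 64% and 50% of eyes score zero at baseline in the insert, loteprednol and monotherapy arms, and the loteprednol arm is 0.0 ± 0.0 at week 8.
- Check the TBUT and IOP baseline rows against source, and settle whether the insert arm's corneal baseline is 0.5 or 0.6.
- Tie the comparative statements in the SAP Discussion and Conclusion to the new estimates and their intervals.

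The cost is SAP wording, a short re-analysis of data already collected, and one degree of freedom per model. That last cost is why a single covariate is enough at 9 to 11 patients per arm.
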